1.4.3.2 Risks related to the administration of fluconazole

Fluconazole (Diflucan[®]) is a market-approved drug. The dose used in this trial (400 mg qd for 13 days) is within the therapeutic range used for patients to treat fungal infections [[R21-2282](#)].

Based on the German ‘Fachinformation’ for Diflucan[®], the following adverse reactions have been observed and reported during treatment with Diflucan with the following frequencies: Very common ($\geq 1/10$); common ($\geq 1/100$ to $< 1/10$); uncommon ($\geq 1/1,000$ to $< 1/100$); rare ($\geq 1/10,000$ to $< 1/1,000$); very rare ($< 1/10,000$), not known (cannot be estimated from the available data).

- Common: Headache, abdominal pain, vomiting, diarrhea, nausea, alanine aminotransferase increased, aspartate aminotransferase increased, blood alkaline phosphatase increased, rash
- Uncommon: Anaemia, decreased appetite, somnolence, insomnia, seizures, paraesthesia, dizziness, taste perversion, vertigo, constipation, dyspepsia, flatulence, dry mouth, cholestasis, jaundice, bilirubin increased, drug eruption, urticarial, pruritus, increased sweating, myalgia, fatigue, malaise, asthenia, fever
- Rare: Agranulocytosis, leukopenia, thrombocytopenia, neutropenia, anaphylaxis, hypercholesterolaemia, hypertriglyceridaemia, hypokalemia, tremor, torsade de pointes, QT prolongation, hepatic failure, hepatocellular necrosis, hepatitis, hepatocellular damage, toxic epidermal necrolysis, Stevens-Johnson syndrome, acute generalized exanthematous-pustulosis, dermatitis exfoliative, angioedema, face oedema, alopecia
- Not known: Drug reaction with eosinophilia and systemic symptoms (DRESS)

Risk mitigation hepatic injury:

- During fluconazole dosing phase laboratory liver parameters will be regularly assessed
- Only subjects with liver parameters AST, ALT and GGT within normal range will be allowed to participate in the trial (see Section [3.3.3](#))
- In case of relevant increase in liver enzymes or hepatic injury (DILI), subjects will discontinue trial treatment (see Section [3.3.4.1](#))

Risk mitigation QT prolongation:

- Subjects with baseline disease (such as pro-arrhythmic conditions) will be excluded from the trial
- No concomitant therapy prolonging the QT interval will be allowed
- During fluconazole dosing phase ECG will be assessed regularly for potential QT prolongation
- Laboratory tests (including determination of potassium levels) will be performed

Risk mitigation dermatological reaction:

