7.3.4 Safety analyses

Safety will be analysed based on the assessments described in Section 2.2.2.2. All treated subjects (TS, refer to Section [7.2](#)) will be included in the safety analysis. Safety analyses will be descriptive in nature and based on BI standards. No hypothesis testing is planned.

For all analyses, the treatment actually administered (= treatment at onset) to the subject will be used (any deviations from the randomised treatment will be discussed in the minutes of the Report Planning Meeting).

Treatments will be compared in a descriptive way. Tabulations of frequencies/proportions will be used to evaluate categorical (qualitative) data, and tabulations of descriptive statistics will be used to analyse continuous (quantitative) data.

Measurements (such as ECG, vital signs, or laboratory parameters) or AEs will be assigned to treatments (see Section [4.1](#)) based on the actual treatment at the planned time of the measurement or on the recorded time of AE onset (concept of treatment emergent AEs). Therefore, measurements planned or AEs recorded prior to first intake of trial medication will be assigned to the screening period, those between first trial medication intake and end of REP (see Section [1.2.3](#)) will be assigned to the treatment period. Events occurring after the REP but prior to next intake or end of trial termination date will be assigned to 'follow-up'. In case of two or more treatments, the follow-up will be summarized according to the previous treatment. These assignments including the corresponding time intervals will be defined in detail in the TSAP. Note that AEs occurring after the last per protocol contact but entered before final database lock will be reported to Pharmacovigilance only and will not be captured in the trial database.

Additionally, further treatment intervals (analysing treatments) may be defined in the TSAP in order to provide summary statistics for time intervals, such as combined treatments, on-treatment totals, or periods without treatment effects (such as screening and follow-up intervals).

Adverse events will be coded using the Medical Dictionary for Regulatory Activities (MedDRA). Frequency, severity, and causal relationship of AEs will be tabulated by treatment, system organ class, and preferred term. SAEs, AESIs (see Section [5.2.5.1.4](#)), and other significant AEs (according to ICH E3) will be listed separately.

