#### **4. CHANGES IN THE PLANNED ANALYSIS OF THE STUDY**

All analyses described in this TSAP are in accordance with the statistical methods described in the CTP.

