## **6. GENERAL ANALYSIS DEFINITIONS**

### **6.1 TREATMENTS**

For basic study information on the treatment to be administered, and selection of dose, cf. Section 4 of the CTP.

Subjects will receive the following two treatments in a fixed sequence (reference treatment always followed by test treatment).

In Period Reference R, all subjects will receive 1 tablet containing

- 10 mg BI 425809 (Reference Treatment R) as a single dose

Afterwards, in Period Test T, all subjects will receive

- 2 capsules, each containing 200 mg Fluconazole, once daily for 13 days (Day -4 to Day 9) and 1 tablet containing 10 mg BI 425809 as a single dose on Day 1 (Test Treatment T).

For statistical analysis of AEs, the following analysis phases are defined for each subject.

Table 6.1: 1 Analysis phases for statistical analysis of AEs, and actual treatment for analysis of laboratory data and vital signs

Study analysis phase	Label	Start	End
Screening 	Screening	Date of informed consent	Date/time of first administration of BI 425809
On treatment	BI 425809	Date/time of first administration of BI 425809	Date/time of first administration of BI 425809 + REP (11 days) or 12:00 a.m. on day after last contact date (whichever occurs first)
Follow-up	F/U BI 425809	Date/time of first administration of BI 425809 + REP (11 days)	Date/time of first administration of Fluconazole or 12:00 a.m. on day after last contact date (whichever occurs first)
On treatment	Fluconazole	Date/time of first administration of Fluconazole	Date/time of second administration of BI 425809 or 12:00 a.m. on day after last contact date (whichever occurs first)
On treatment	BI + Fluconazole	Date/time of second administration of BI 425809	Date/time of second administration of BI 425809 + REP (14 days) or 12:00 a.m. on day after last contact date (whichever occurs first)
Follow-up	F/U BI + Fluconazole	Date/time of second administration of BI 425809 + REP (14 days)	12:00 a.m. on day after last contact date

 See [Section 6.7](#) for definition of baseline, which will be used in the statistical analyses of safety laboratory data and vital signs.

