The on-treatment phase for 'BI + Fluconazole' includes both the REP for BI 425809 (14 days) and Fluconazole (6 days). Since the second administration of BI 425809 is scheduled at 9:00 am on Visit 3, Day 1, while the last administration of Fluconazole is scheduled at 8:00 am on the Visit 3, Day 9 (see CTP, Flow chart). Therefore, Date/time of the second administration of BI 425809 + REP (14 days) is one hour after Date/time of the last administration of Fluconazole + REP (6 days).

AE summary tables will present results for the on-treatment phases only. All AEs will be listed.

In AE tables in CTR Section 15.3 (but not in Appendix 16.1.13.1.8.1 and Appendix 16.1.13.1.8.2 AE tables), the following totals will be provided in addition:

- **"Total BI"**, defined as the total over all on-treatment phases involving BI 425809
- **"Total Fluconazole"**, defined as the total over all on-treatment phases involving Fluconazole
- **"Total on-trt"**, defined as the total over all on-treatment phases

Safety laboratory data, vital signs and PK parameters will be analyzed based on treatment periods (BI 425809 and BI+Fluconazole) with clear differentiation between baseline (cf. [Section 6.7](#)) and post-baseline measurements. Measurements will be considered on-treatment, if they were taken within the on-treatment phases of BI 425809 or BI+Fluconazole as defined in [Table 6.1: 1](#). More details on the technical implementation of these analyses are provided in the ADS Plan of this TSAP.

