## **6.7 BASELINE, TIME WINDOWS AND CALCULATED VISITS**

For both periods, the last available value determined prior to administration of BI 425809 will be defined as baseline.

Time windows are defined in Section 6.1 of the CTP. Adherence to time windows will be checked at the Report Planning Meeting.

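### SAP 6.1 omits the fluconazole-alone phase from the on-treatment definition for laboratory data, so the Day -1 liver panel has no role and an early rise is absorbed into the period-T baseline

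*SAP*

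**What the plan says.** SAP 6.1 divides each subject's time into analysis phases in Table 6.1: 1, titled "Analysis phases for statistical analysis of AEs, and actual treatment for analysis of laboratory data and vital signs". Three phases are labelled on treatment: BI 425809, Fluconazole, and BI + Fluconazole. The Fluconazole phase starts at the first fluconazole dose and ends at "Date/time of second administration of BI 425809 or 12:00 a.m. on day after last contact date (whichever occurs first".

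The text below the table is narrower for laboratory data. It says "Safety laboratory data, vital signs and PK parameters will be analyzed based on treatment periods (BI 425809 and BI+Fluconazole", and then "Measurements will be considered on-treatment, if they were taken within the on-treatment phases of BI 425809 or BI+Fluconazole". The Fluconazole phase is not named. For adverse events, the same section includes that phase in the fluconazole total and in the on-treatment total.

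SAP 6.7 sets the reference value: "For both periods, the last available value determined prior to administration of BI 425809 will be defined as baseline". SAP 7.8.2 plans descriptive statistics of laboratory values over time, differences from baseline, and a shift table from baseline to the last on-treatment value.

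Protocol 7.3.4 assigns measurements and events "based on the actual treatment at the planned time of the measurement or on the recorded time of AE onset", and leaves the detailed time intervals to the SAP. SAP section 4 declares no departure: "All analyses described in this TSAP are in accordance with the statistical methods described in the CTP". Protocol 1.4.3.2 names as a hepatic safeguard that "During fluconazole dosing phase laboratory liver parameters will be regularly assessed".

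**The concern.** Fluconazole is one of the two investigational products. Protocol 2.2.2.3 says that the safety of both products will be assessed, with laboratory tests among the measures. Its known hepatic effects are the reason for the frequent liver panels in period T. The SAP treats the days on fluconazole alone as on treatment for adverse events but not for laboratory values, and gives no reason for the difference.

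Two things are at stake. First, the period-T laboratory tables show change from a value taken after several days of fluconazole. They therefore describe what happens after BI 425809 is added to fluconazole, and no planned table shows the change since fluconazole was started. Second, a subject whose enzymes rise early enough to stop treatment before the second BI 425809 dose has no entry in the period-T change or shift tables.

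**Working it through.** The plan gives no figure to reproduce here, so the check places each scheduled period-T liver panel in the phases of Table 6.1: 1.

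**Inputs.** Planned times come from the protocol Flow Chart for Treatment T, in hours from the second BI 425809 dose. Laboratory sets B and C both contain AST, ALT, alkaline phosphatase and GGT (protocol Table 5.2.3: 1). Phase limits come from SAP Table 6.1: 1 and the baseline rule from SAP 6.7.

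**Windows.** The Fluconazole phase runs from -97 h to 0 h. The BI + Fluconazole phase runs from 0 h to 14 × 24 = 336 h. As a check, the last fluconazole dose at 191 h plus a residual effect period (REP) of 6 × 24 = 144 h gives 335 h. That is one hour before 336 h, as SAP 6.1 states.

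**Placement.**

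| Panel | Hours | Phase | Role under the SAP |
|---|---|---|---|
| Day -1, set C | -25 | Fluconazole | neither baseline nor on-treatment |
| Day 1 pre-dose, set B | -2 | Fluconazole | period-T baseline |
| Day 2, set B | 24 | BI + Fluconazole | on-treatment |
| Day 4, set C | 71 | BI + Fluconazole | on-treatment |
| Day 6, set C | 119 | BI + Fluconazole | on-treatment |
| Day 8, set C | 167 | BI + Fluconazole | on-treatment |

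The six panels split into 1 unplaced, 1 used as baseline and 4 on-treatment. The end-of-trial panel (Day 16 at the earliest, 15 × 24 = 360 h) falls after 336 h and is follow-up.

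**Fluconazole doses before each early panel.** The Day -1 sample may be taken up to 15 minutes early but not late (protocol 6.1). It therefore follows the doses at -97, -73 and -49 h, which is three doses. The Day 1 sample is completed before that day's fluconazole dose, so it follows those three and the dose at -25 h, which is four.

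**Effect on change from baseline.** Let x0 be a pre-fluconazole value, x1 the Day 1 pre-dose value and x2 a later value. The SAP reports x2 - x1. The change over the fluconazole period is x2 - x0 = (x2 - x1) + (x1 - x0). The term x1 - x0 appears in no planned change table. In the shift table, a subject already above range on Day 1 starts in the high category.

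**Vital signs.** None is scheduled on Days -4 to -1. The only scheduled measurement in the Fluconazole phase is Day 1 pre-dose, which is the baseline.

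**Subject stopped on fluconazole alone.** Protocol 3.3.4.1 contains liver criteria that could apply at this stage. One uses a next-day control sample, so a Day -1 finding would be rechecked on Day 1. Without a second BI 425809 dose there is no administration to define a period-T baseline, and there is no BI + Fluconazole phase. The subject's Fluconazole phase runs to the day after last contact, so his end-of-trial panel falls in it and is not on-treatment either. With 15 subjects planned, each such stop removes 1/15 = 6.7% from the period-T change and shift tables. The documents give no expected rate.

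**Available pre-fluconazole value.** No laboratory test is scheduled on Day -4. The last one before fluconazole is period 1 Day 10, set C, at 215 h after the first BI 425809 dose. With the minimum 16-day separation, the first fluconazole dose comes at 384 - 97 = 287 h, so the gap is at least 287 - 215 = 72 h. That sample lies inside the first BI 425809 on-treatment phase (11 × 24 = 264 h). It is therefore free of fluconazole but not of BI 425809.

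**The case against.** The strongest reply is that little is lost in a small descriptive trial. All individual values are listed, and out-of-range and possibly clinically significant values are highlighted. Clinically relevant findings become adverse events. Events in the Fluconazole phase are tabulated, and hepatic injury has its own table. A subject stopped early stays in the treated set, and his period-R values are summarised. All of this stands. A reader might infer that such a subject is hidden from the report or that the safety picture is biased, but the documents do not support that. What is missing is his contribution to the period-T change and shift summaries.

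A reader might also infer that every fluconazole-alone liver test drops out, or that vital signs do. Neither follows: Day 1 pre-dose stays in the summaries as baseline, and no scheduled vital sign is lost. Day -1 may still appear in the values-over-time table, which has no stated on-treatment limit. The ADS Plan, to which SAP 6.1 defers technical details, is not available to settle this. For a subject who completes period T, adding Day -1 would not alter the last on-treatment value.

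Day 1 pre-dose is also a sensible baseline for isolating the addition of BI 425809 to fluconazole. That is right, and it should be kept for that column. It does not supply the missing fluconazole comparison.

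Finally, protocol 7.3.4 lets the SAP define the intervals, so the difference is better called unreconciled than a breach. The inconsistency within SAP 6.1 remains.

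On adverse events, a reader might infer that the open-ended Fluconazole phase loses events when there is no second BI 425809 dose. It does the reverse, because events up to last contact count as on-treatment and stay in the summary tables.

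**Conclusion.** The point holds in a limited form. The text of SAP 6.1 contradicts its own Table 6.1: 1 and does not carry through the actual-treatment rule of protocol 7.3.4. One of six scheduled liver panels during fluconazole dosing has no defined role. A second serves only as a baseline taken after four doses. A subject stopped on fluconazole alone is absent from the period-T change and shift tables.

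This rests on reading the SAP text as the operative rule, since the ADS Plan cannot be checked. It also rests on the Flow Chart times; unscheduled samples could add values. The early stop is a possibility, not a forecast. The primary and secondary pharmacokinetic analyses are unaffected. The change is worth making because these liver values are part of the protocol's stated hepatic safeguard and the repair needs no new data.

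**What to change.** 1. In SAP 6.1, add the Fluconazole phase to the on-treatment definition for laboratory data, and for any unscheduled vital signs, and report it as its own column.
2. In SAP 6.7, define a reference for that column and for a change or shift summary over the whole fluconazole period: the last value before the first fluconazole dose. For liver enzymes this is scheduled at period 1 Day 10, set C. State that it falls within the first BI 425809 on-treatment phase. Set C has no bilirubin, so the last scheduled pre-fluconazole bilirubin is period 1 Day 2, set B.
3. Keep Day 1 pre-dose as baseline for the BI + Fluconazole column. State that the same value also counts as on-treatment in the Fluconazole column, so that the two roles are not confused.
4. Secondary: for a subject with no second BI 425809 dose, reconcile the end of the Fluconazole phase in Table 6.1: 1 with the 6-day fluconazole REP in SAP 6.1 and the follow-up rule in protocol 7.3.4. Ending the phase earlier would move later events out of the on-treatment adverse event tables and could move the end-of-trial panel out of the on-treatment data. The choice should be stated with its reason.

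The cost is SAP wording, one more column and a second reference value in the laboratory tables, with the programming that goes with them. No additional samples or visits are needed.

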## **6.2 IMPORTANT PROTOCOL DEVIATIONS**

Consistency check listings (for identification of deviations from time windows) and a list of protocol deviations (e.g. deviations in drug administration, in blood sampling times, etc.) will be provided to be discussed at the Report Planning Meeting. At this meeting, it will be decided whether a discrepant data value can be used in analyses or whether it must be corrected in the clinical database. Each protocol deviation must be assessed to determine whether it is an important PD (iPD). For definition of iPDs, and for the process of identification of these, refer to the BI reference document "Identify and Manage Important Protocol Deviations (iPD)" ([2](#)) and the DV domain template.

If any iPDs are identified, they are to be summarised into categories and will be captured in the decision log. Categories which are considered to be iPDs in this trial are defined in the DV domain template. If the data show other iPDs, the definition in the DV domain template will be supplemented accordingly by the time of the Report Planning Meeting.

iPDs will be summarized and listed. Which kind of iPDs could potentially lead to exclusion from which analysis set is specified in the DV domain template. The decision on exclusion of subjects from analysis sets will be made at the latest at the Report Planning Meeting, after discussion of exceptional cases and implications for analyses.

Non-important COVID-19 related PDs will only be listed.

## **6.3 SUBJECT SETS ANALYSED**

The treated set (TS) and pharmacokinetic parameter analysis set (PKS) will be used as defined in the CTP, Section 7.3.

Table 6.3: 1 Subject sets analyzed

Class of endpoint	Subject set	
	TS	PKS
Disposition	X	
iPDs	X	
Primary endpoints		X
Secondary PK endpoints		X
Further PK endpoints		X
Safety parameters	X	
Demographic/baseline characteristics	X	
Treatment exposure	X	

## 6.5 POOLING OF CENTRES

This section is not applicable, because the study was performed in only one center.

## 6.6 HANDLING OF MISSING DATA AND OUTLIERS

**CTP:** “If a subject is removed from or withdraws from the trial prior to the administration of trial medication, the data of this subject will not be entered in the case report form (CRF) and will not be reported in the clinical trial report (CTR). If a subject is removed from or withdraws from the trial after the administration of trial medication, this will be documented and the reason for discontinuation must be recorded in the CRF. In addition, the data will be included in the CRF and will be reported in the CTR.”

**CTP:** “It is not planned to impute missing values for safety parameters.”

One exception where imputation might be necessary for safety evaluation is AE dates. Missing or incomplete AE dates are imputed according to BI standards (3).

Missing data and outliers of PK data are handled according to BI standards.

**CTP:** “Pharmacokinetic parameters that cannot be reasonably calculated based on the available drug concentration-time data will not be imputed.”

## **6.7 BASELINE, TIME WINDOWS AND CALCULATED VISITS**

For both periods, the last available value determined prior to administration of BI 425809 will be defined as baseline.

Time windows are defined in Section 6.1 of the CTP. Adherence to time windows will be checked at the Report Planning Meeting.

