			7:00	16:00	Light snack (voluntary)						
			8:00	17:00			x				x
			10:00	19:00	Dinner						
			12:00	21:00			x				x
		2	23:00	08:00	Fluconazole administration			x ⁷			x
			24:00	09:00	Breakfast (voluntary) ³ , discharge from trial site	B	x		x	x	x
		3	47:00	08:00	Fluconazole administration ⁶		x	x			x
		4	71:00	08:00	Fluconazole administration ⁶	C	x				x
		5	95:00	08:00	Fluconazole administration						x
		6	119:00	08:00	Fluconazole administration ⁶	C	x				x
		7	143:00	08:00	Fluconazole administration						x
		8	167:00	08:00	Fluconazole administration ⁶	C	x		x		x
		9	191:00	08:00	Fluconazole administration						x
		10	215:00	08:00	Ambulatory visit		x				x
FU	4	16 to 30			End of trial (EoTrial) examination ⁴	D			x	x	x

1. See [Flow Chart](#) on previous page.
2. The time is approximate; the procedure is to be performed and completed within the 2 h prior to fluconazole drug administration.
3. If several actions are indicated at the same time, the intake of meals will be the last action.
4. At the end of trial visit the EoTrial examination includes physical examination, vital signs, ECG, safety laboratory, recording of AEs and concomitant therapies.
5. AEs and concomitant therapies will be recorded throughout the trial, but will be specifically asked for at the times indicated in the Flow Chart above.
6. Immediately after PK blood sampling.
7. PK sampling pre-dose (tolerance with respect to planned time: -5 min); fluconazole administration on time.
8. Letters A, B, C and D define different sets of safety laboratory examinations (for details refer to Section [5.2.3](#)).
9. Including urine drug screening and alcohol breath test

TABLE OF CONTENTS

TITLE PAGE	1
CLINICAL TRIAL PROTOCOL SYNOPSIS	2
FLOW CHART	4
TABLE OF CONTENTS	6
ABBREVIATIONS	10
1. INTRODUCTION.....	13
1.1 MEDICAL BACKGROUND	13
1.2 DRUG PROFILE	13
1.2.1 BI 425809	13
1.2.1.1 Non-clinical drug safety.....	13
1.2.1.2 Clinical Safety in Healthy Subjects	14
1.2.1.3 Expected exposure of BI 425809 in this trial.....	15
1.2.2 Fluconazole	16
1.2.3 Residual Effect Period	19
1.3 RATIONALE FOR PERFORMING THE TRIAL	19
1.4 BENEFIT - RISK ASSESSMENT	19
1.4.1 Expected benefit for the target population	19
1.4.2 Procedure-related risks	20
1.4.3 Drug-related risks and safety measures.....	20
1.4.3.1 Risks related to the administration of BI 425809	20
1.4.3.2 Risks related to the administration of fluconazole.....	21
1.4.3.3 Drug-induced liver injury	22

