1.2.1.3 Expected exposure of BI 425809 in this trial

1.2.2 Fluconazole

Fluconazole is a triazole antifungal agent. Its primary mode of action is the inhibition of fungal cytochrome P-450-mediated 14 alpha-lanosterol demethylation, an essential step in fungal ergosterol biosynthesis. The accumulation of 14 alpha-methyl sterols correlates with the subsequent loss of ergosterol in the fungal cell membrane and may be responsible for the antifungal activity of fluconazole [[R21-2282](#)].

Pharmacokinetics and drug metabolism

After oral administration fluconazole is well absorbed, and plasma levels (and systemic bioavailability) are over 90% of the levels achieved after intravenous administration. Oral absorption is not affected by concomitant food intake. Peak plasma concentrations in the fasting state occur between 0.5 and 1.5 hours post-dose. Ninety percent steady state levels are reached by day 4-5 with multiple once daily dosing.

Fluconazole achieves good penetration in all body fluids studied. High skin concentration of fluconazole, above serum concentrations, are achieved in the stratum corneum, epidermis-dermis and eccrine sweat. Fluconazole accumulates in the stratum corneum.

Fluconazole is metabolised only to a minor extent. Plasma elimination half-life for fluconazole is approximately 30 hours. The major route of excretion is renal, with approximately 80% of the administered dose appearing in the urine as unchanged medicinal product. Fluconazole clearance is proportional to creatinine clearance. There is no evidence of circulating metabolites.

Fluconazole is a moderate inhibitor of the isozymes CYP2C9 and CYP3A4: Concomitant intake of fluconazole 200 mg and midazolam (a CYP3A4 substrate) 7.5 mg orally increased the midazolam AUC and half-life 3.7-fold and 2.2-fold, respectively [[R21-2282](#)], similar results were found in [[R03-2551](#)]. Fluconazole is also a strong inhibitor of the isozyme CYP2C19 [[R21-2282](#)].

Clinical safety in healthy volunteers:

For an overview of safety when fluconazole was used as a moderate inhibitor in healthy volunteer trials, a number of publications is cited here which use different treatment schedules for fluconazole ranging from

- administration of fluconazole (400 mg on day 1 and 200 mg qd on subsequent days) over 4 days in Scott et al. [[R21-2438](#)], over 7 days in Gupta et al. [[R21-2439](#)] or over 20 days in Gardin et al. [[R21-2467](#)],

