2.2.2.3 Safety and tolerability

Safety and tolerability of BI 425809 and fluconazole will be assessed based on:

- Adverse events (including clinically relevant findings from the physical examination)
- Safety laboratory tests
- 12-lead ECG
- Vital signs (blood pressure, pulse rate)

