3. DESCRIPTION OF DESIGN AND TRIAL POPULATION

3.1 OVERALL TRIAL DESIGN AND PLAN

The study will be performed as a non-randomised, open-label, 2-period fixed-sequence crossover trial in healthy male subjects in order to compare the Test Treatment (T) to the Reference Treatment (R). An overview of both treatments is given below, for details refer to Section [4.1](#).

Reference Treatment, R

- One 10 mg tablet BI 425809 given alone on Day 1 of period 1

Test Treatment T

- One 10 mg tablet BI 425809 given one hour after the administration of fluconazole on Day 1 of period 2; dosing with fluconazole will start from Day -4 (pre administration of BI 425809) and will continue through Day 9 (post administration of BI 425809); dosing regimen for fluconazole is 400 mg qd

Treatments with BI 425809 will be given under fasting conditions. Reference Treatment will always be followed by the Test Treatment in a fixed sequence. The treatment periods will be separated by a wash-out phase of at least 16 days between the administrations of BI 425809.

[figure not shown]

Figure 3.1: 1 Trial design

An overview of all relevant trial activities is provided in the [Flow Chart](#). For visit schedule and details of trial procedures at selected visits, refer to Sections [6.1](#) and [6.2](#), respectively.

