4.1.1 Identity of the Investigational Medicinal Products

[REDACTED]	
[REDACTED]	[REDACTED]
[REDACTED]	
[REDACTED]	[REDACTED]
[REDACTED]	[REDACTED]
[REDACTED]	[REDACTED]
[REDACTED]	[REDACTED]
[REDACTED]	[REDACTED]
[REDACTED]	[REDACTED]

The characteristics of the investigational medicinal product fluconazole are:

Name:	Diflucan®
Substance:	Fluconazole
Pharmaceutical formulation:	Hard capsule
Source:	[REDACTED]
Unit strength:	200 mg
Posology:	2-0-0
Route of administration:	oral
Duration of use:	13 days (Day -4 to Day 9) in Visit 3 (Test Treatment)

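### The Treatment T safety baseline is taken after four fluconazole doses, so change-from-baseline and shift tables omit any fluconazole effect already present by then

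*SAP*

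**What the plan says.** SAP 6.7 gives the rule: "For both periods, the last available value determined prior to administration of BI 425809 will be defined as baseline". SAP 7.8.2 and 7.8.3 use this baseline for laboratory and vital-sign differences. SAP 7.8.2 also uses it for the frequency tables comparing baseline with the last on-treatment value against the reference range.

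In Treatment T, protocol 3.1 states that "dosing with fluconazole will start from Day -4 (pre administration of BI 425809) and will continue through Day 9", and that the "dosing regimen for fluconazole is 400 mg qd". Protocol 4.1.1 gives the duration as "13 days (Day -4 to Day 9) in Visit 3 (Test Treatment"). The Treatment T Flow Chart schedules laboratory set B and vital signs on Day 1 before dosing. Its footnote 2 says "the procedure is to be performed and completed within the 2 h prior to fluconazole drug administration".

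Protocol 2.2.2.3 states the safety aim for both drugs: "Safety and tolerability of BI 425809 and fluconazole will be assessed based on" adverse events, laboratory tests, ECG and vital signs. Protocol 1.4.3.2 lists raised ALT, AST and alkaline phosphatase as common with fluconazole and makes regular liver tests part of the risk mitigation.

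SAP Table 6.1: 1 labels the interval from first fluconazole to second BI 425809 as on treatment. The text below the table, however, counts laboratory values and vital signs as on-treatment only in the BI 425809 and BI + Fluconazole phases.

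**The concern.** A baseline should normally precede the drugs whose effect the change score is meant to show. In Treatment R it does. In Treatment T it precedes BI 425809 but not fluconazole, so two columns headed change from baseline have different meanings: change from a drug-free state in R, and change from an on-fluconazole state in T. Nothing in the SAP tells the reader this.

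A laboratory value or pulse rate that moved between Day -4 and Day 1 enters the Treatment T tables as a starting value, not as a change. An enzyme above the reference range on Day 1 is tabulated as high at baseline. The fluconazole-only interval has no summary of its own to make up for this: its one scheduled laboratory sample, set C on Day -1, is superseded as baseline by Day 1 set B and lies outside the on-treatment phases used for laboratory data. The SAP provides no fluconazole-free reference for Treatment T.

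**Working it through.** **Inputs**
- Fluconazole dose times relative to BI 425809 (Flow Chart): -97, -73, -49, -25, -1, 23, 47, 71, 95, 119, 143, 167 and 191 h, which makes 13 doses.
- Baseline sample: about -2 h (Flow Chart).
- Fluconazole half-life: about 30 h (protocol 1.2.2). As an assumption to show sensitivity, 24 to 36 h.
- BI 425809 half-life: about 44 h (protocol 3.2).

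**The protocol's own figure.** Protocol 1.2.2 says "Ninety percent steady state levels are reached by day 4-5 with multiple once daily dosing". With first-order accumulation, the time to 90% is 30 × log2(10) = 99.7 h, or 4.2 days. This agrees.

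**Doses around the baseline.** Four doses (-97 to -25 h) precede it and nine (-1 to 191 h) follow: 4/13 = 31% and 9/13 = 69%.

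**Plasma level at baseline.** After four doses 24 h apart, the trough as a fraction of steady state is 1 - 2^(-96/30) = 0.891. For half-lives of 36 and 24 h it is 0.843 and 0.938.

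**Exposure before baseline.** In a one-compartment model, the exposure delivered by time t, in dose-equivalents, is the sum over doses already given of 1 - 2^(-(t - t_dose)/30).
- At -2 h: 0.889 + 0.806 + 0.662 + 0.412 = 2.77. As a share of all 13 doses, 2.77/13 = 21% (20% to 23% over the half-life range). About 79% comes later.
- At 24 h: 0.939 + 0.894 + 0.815 + 0.678 + 0.439 + 0.023 = 3.79. Of this, 2.77/3.79 = 73% precedes the baseline.

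**What follows the baseline, by parameter**
- AST, ALT, alkaline phosphatase and GGT: set B on Day 2 and set C on Days 4, 6 and 8, all while fluconazole continues. These samples can show an effect that builds with time.
- All other laboratory values: set C does not contain them (protocol Table 5.2.3: 1), so the only scheduled on-treatment sample after baseline is set B at 24 h. The end-of-trial visit on Days 16 to 30 falls after the 14-day residual effect period. The change score covers about 26 h, and four of the six fluconazole doses given by 24 h come before it.
- Vital signs: as the extracted Flow Chart reads, they also stop at 24 h until follow-up. Column positions may be shifted.

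**Fluconazole-free values already collected**
- Treatment R Day 1 pre-dose: set B and vital signs, free of both drugs. With the minimum wash-out it is 16 × 24 - 97 = 287 h, about 12 days, before first fluconazole, and at least 16 days before the Treatment T dose of BI 425809.
- Treatment R Day 10: set C at 215 h. This is inside the 11-day (264 h) BI 425809 on-treatment phase of SAP Table 6.1: 1, with 2^(-215/44) = 3.4% of BI 425809 remaining.

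**A related inconsistency.** Protocol 6.1 allows Day 1 pre-dose procedures within 3 h before BI 425809 (06:00 to 09:00). Flow Chart footnote 2 restricts them to the 2 h before fluconazole (06:00 to 08:00). Under the former, a baseline could follow the fifth dose.

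**The case against.** The strongest defence is that the rule answers a coherent question. Applied alike in both periods, it measures change after BI 425809 alone and change after BI 425809 added to fluconazole. A pre-fluconazole baseline would mix the two drugs' effects in Treatment T. This stands, and it is why the existing baseline should be kept.

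It is also true that little is hidden. Absolute values over time, reference-range comparisons, possibly clinically significant values and individual listings do not use this baseline. The hepatic injury and discontinuation criteria are multiples of the upper limit of normal. AEs have a separate Fluconazole phase from the first fluconazole dose. Exclusion criterion 25 bars subjects with confirmed AST, ALT or GGT above normal at screening, so a high Day 1 enzyme would stand out. All of this limits the consequence, but it leaves the change and shift tables as they are. The ADS Plan, which SAP 6.1 cites for technical detail, is not available here.

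A reader might infer from the 89% that the tables omit most of the fluconazole effect. The documents do not support that. The figure is a share of trough concentration, not of effect. It would carry over only to an effect that follows plasma level closely. For an effect that builds with dose or time, 69% of doses and about 79% of exposure come after the baseline. Even the 73% for parameters last sampled at 24 h is a share of exposure.

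Another tempting step is to replace the baseline with the last value before fluconazole, which for liver enzymes is Treatment R Day 10. By the SAP's own definition that value is on-treatment for BI 425809. It is also the last scheduled Treatment R liver value, so a rise in R would be absorbed into the baseline for T.

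**Conclusion.** The point holds in a limited form. Treatment T changes from baseline and shift tables omit any laboratory or vital-sign effect of fluconazole already present after four doses, when the trough is about 89% of steady state (84% to 94% for assumed half-lives of 36 to 24 h). The Day -1 liver panel is normally neither baseline nor on-treatment. How much of the effect this amounts to cannot be determined from the documents. The gap is narrower for the four liver enzymes, which are sampled to Day 8, than for the parameters whose last on-treatment sample is at 24 h.

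This rests on the Flow Chart columns as extracted, on first-order accumulation, and on the Day 1 sample being drawn before the fifth dose. The primary and secondary PK endpoints are unaffected, no decision rule uses change from baseline, and safety is descriptive. Severity is minor to moderate.

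**What to change.** - In SAP 6.7, keep the current baseline for the question of BI 425809 added to fluconazole, but label it in Treatment T tables as *on fluconazole, before BI 425809*.
- In SAP 6.7, 7.8.2 and 7.8.3, add supplementary Treatment T summaries against the Treatment R Day 1 pre-dose value: change from baseline and a shift table for laboratory values, and change from baseline for vital signs.
- Do not use Treatment R Day 10 as the reference.
- In SAP 6.1 and 7.8.2, summarise the Day -1 set C values as a fluconazole-only time point.
- Reconcile Flow Chart footnote 2 with the window in protocol 6.1, so that the baseline's position relative to the fifth dose is unambiguous.

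The cost is SAP wording, one more baseline flag and a few more tables, with no new data. The drawback is a reference value at least 16 days older than Treatment T Day 1. The supplementary changes would also combine both drugs' effects once BI 425809 is given, so they should be read beside the existing display.
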